## 14.2 Secondary Endpoints

### 14.2.1 Continuous Secondary Endpoints

The secondary endpoints that will be treated as continuous (all endpoints derived from “ON/OFF” home diaries, UDysRS questionnaire and UPDRS questionnaire part 2 and 3) will be analyzed with MMRMs similar to the one used for the primary endpoint. The baseline value of the analysis variable in question will be used as the baseline covariate in the MMRM. The analyses will be performed in the EE1 and EE2 set. In addition to Visit 7, data from Visits 3, 4, 5 and 6 will be analyzed as well.

For “ON/OFF” home diaries, in addition to the secondary endpoints, also ON time with troublesome dyskinesia and ON time with ON time with non-troublesome dyskinesia will be analyzed as well.

For UDysRS, all four sum scores (Part 1, Part 2, Part 3 and Part 4), Individual parts.

## 15 Analysis of Safety and Tolerability

### 15.1 Extent of Exposure

The following information will be summarized by treatment group and overall using the Safety Population.

## Statistical Analysis Plan

The summary include either a tabulation of number (and %) of subjects or descriptive statistics (for durations and total exposure).

The number of subjects exposed to study treatment and summary statistics on duration of exposure (Mean, SD, etc.) by each of the 4 treatment groups (placebo, 100 mg BID, 150 mg BID, pridopidine total) – in titration period (all subjects, subjects with 2 weeks titration, subjects with 4 weeks titration), in maintenance period (all subjects, subjects with 2 weeks titration, subjects with 4 weeks titration)

### 15.2 Compliance

Subjects will be instructed to bring with them the used and unused drug kits at Visit 3, Visit 5, Visit 6, Visit 7/ET, and at Visit 8/FU, in which treatment compliance will be evaluated. Treatment compliance at the Visit 3, Visit 5, Visit 6, Visit 7/ET, and Visit 8/FU and overall for the 14 week active treatment period will be calculated using the following formula:

$$\text{Compliance (\%)} = [\text{Total number of administered doses} / \text{Total number of scheduled doses}] \times 100$$

The total number of scheduled doses will be calculated based on the extent (days) of exposure of each subject. A range between 80% to 120% will be taken as reference limits for a satisfactory level of compliance. The compliance (expressed as %) will be summarized with descriptive statistics by treatment group. In addition, the number (and %) of subjects with compliance between 80% to 120% will be tabulated by treatment group.

### 15.3 Adverse Events

All AEs will be coded using MedDRA version 21.0. Treatment-emergent adverse events (TEAEs) are defined as all AEs that start or increase in severity after the subject receives the first dose of study drug. Events with a missing start time, but with a start date equal to the date of first dose of study drug will be considered treatment-emergent. If the AE start date is incomplete, it will be imputed as follows for the purpose of determining TEAE:

- If the start date is completely missing, the start date will be equal to the date of the first dose of study drug. However, if the stop date is not missing and is before the date of the first dose of study drug, then the stop date will be used instead.
- If the start day is missing, the first day of the month will be used.
- If the start day and month are missing, then the first day of the first month (January) will be used.
- If the end date is completely missing, the latest end date of any other adverse event, or the date of last study visit for the same subject will be used, whichever occurs later.
- If the end day is missing, the last day of the month will be used.
- If the end day and month are missing, then the last day of the month of the last study visit for the same subject will be used.

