6.5.1.3 Eliciting and Documenting Adverse Events

Adverse events will be assessed beginning at enrollment (date of signed informed consent) and up to visit of the safety follow-up period (Visit 8).

Serious AEs that occur more than 30 days after the reporting period need not be reported unless the investigator considers them related to study treatment.

At every study visit, patients will be asked a standard nonleading question to elicit any medically related changes in their well-being. Patients will also be asked if they have been hospitalized, had any accidents, used any new medications, or changed concomitant medication regimens (both prescription and OTC medications).

In addition to patient observations, any abnormal laboratory test results (haematology, clinical chemistry, or urinalysis) or other safety assessments (e.g., ECGs, radiological scans, vital sign measurements), including those that worsen from Visit 2, felt to be clinically significant in the medical and scientific judgment of the investigator are to be recorded as AEs or SAEs. In addition, AEs identified from review of other documents (e.g., patient diaries) that are relevant to patient safety will be documented on the AE page in the eCRF.

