### 4 Design and Type of the Study

The study was originally designed as a 16-week study with a 2 week titration phase (January 24th, 2019 original protocol, v1.1) and was modified on 15th October 2019 (Amendment 1) via Safety Urgent Measures letter to increase the titration period from 2 to 4 weeks. This change along with other changes were implemented in Amendment 1 (19th November 2019, v2.0). The duration of the study was thus increased from 16 to 18 weeks.

The study was designed as a Phase 2b, multicenter, randomized, double-blind, placebo-controlled, three-arm, parallel-group study to evaluate the efficacy, safety, and PK of pridopidine 100 mg BID and 150 mg BID vs placebo for the treatment of PD LID.

Due to COVID-19 the study was terminated early and is now considered a Phase 2 proof of concept (PoC) study. The study will evaluate efficacy and safety of the two doses of pridopidine vs placebo as well as the pooled active doses vs. placebo.

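### The SAP's rule for partial AE start dates ignores the first-dose date, so on-treatment events in the first-dose month (or year) can be classed as pre-treatment and TEAEs may be under-counted

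*SAP*

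**What the plan says.** SAP 15.3 (Adverse Events) defines TEAEs as "all AEs that start or increase in severity after the subject receives the first dose of study drug". It then gives imputation rules with a stated purpose: "If the AE start date is incomplete, it will be imputed as follows for the purpose of determining TEAE".

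The three start-date rules are:

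- Nothing known: "If the start date is completely missing, the start date will be equal to the date of the first dose of study drug". A stop date before first dose overrides this.
- Month and year known: "If the start day is missing, the first day of the month will be used".
- Only the year known: "If the start day and month are missing, then the first day of the first month (January) will be used".

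A tie rule covers the day of first dose: "Events with a missing start time, but with a start date equal to the date of first dose of study drug will be considered treatment-emergent".

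Only the first of the three refers to first dose or to the stop date. No other part of the SAP or protocol adds a lower limit at first dose, or a default of treatment-emergent when in doubt. Protocol 6.5.1.3 has AEs collected from informed consent, so the database will hold pre-dose events as well as on-treatment ones.

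**The concern.** The imputed date decides which side of first dose an event falls on. Setting it to the start of the month or year, without checking when dosing began, puts it before dosing for almost every patient whenever the known part of the date matches first dose. The rules are also inconsistent with each other: an event with no date information is kept as a TEAE, while one known to have started in the first-dose month is not.

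Safety and tolerability are a stated objective (SAP 3.3). The incidence table by system organ class and preferred term, and most rows of the AE overview, count TEAEs only, so a reclassified event disappears from those summaries. Under the day-missing rule the events at risk are mostly those of the titration weeks. SAP section 4 records that titration was lengthened from 2 to 4 weeks through an urgent safety letter.

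**Working it through.** The plan states no figure on this point, so there is none to reproduce. The check is date logic followed by a count.

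**Inputs.** The TEAE definition, the three start-date rules and the tie rule are from SAP 15.3. Active treatment under Amendment 1 is 16 weeks, or 16 × 7 = 112 days (Protocol 3.1.2). Total time from first dose to last visit is 112 days under the original protocol and 18 × 7 = 126 days under the amendment (SAP section 4: "The duration of the study was thus increased from 16 to 18 weeks"). Titration is 2 or 4 weeks (SAP 4.2). Fewer than 30 patients were enrolled (SAP 9.3), randomized 1:1:1 (SAP 4.2). Assumptions: first-dose dates are spread evenly over a 365-day year, and every onset day is equally likely.

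**Step 1: the logic.** Let F be the first-dose date and T the true onset, on or after F.

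- Day missing, T in the same month as F: the imputed date is the 1st of F's month. This is before F unless F is itself the 1st, when the tie rule makes the event a TEAE. The rule fails for 365 − 12 = 353 of 365 first-dose dates.
- Day missing, T in a later month: the imputed date is after F. Correct.
- Day and month missing, T in the same year as F: the imputed date is 1 January, before F unless F is 1 January. The rule fails for 364 of 365 first-dose dates.
- Day and month missing, T in a later year: correct.

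Example: first dose 15 June, onset 20 June, recorded as June only. The imputed start is 1 June, so the event is pre-treatment. Had the date been left entirely blank, it would have been set to 15 June and counted as a TEAE.

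**Step 2: day-missing rule.** In a month of n days, first dose on day d (2 to n) leaves n − d + 1 affected onset days, which sum to n(n − 1)/2. Over the year: 7 × 465 + 4 × 435 + 1 × 378 = 5,373.

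- Days 1–112: 5,373 / (365 × 112) = 5,373 / 40,880 = 13.1%.
- Days 1–126: 5,373 / 45,990 = 11.7%.
- Days 1–28: capping each patient at 28 days removes 3 days in each 31-day month and 1 in each 30-day month (7 × 3 + 4 × 1 = 25). That leaves 5,348 / (365 × 28) = 5,348 / 10,220 = 52.3%.

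Of the affected days, 5,348 / 5,373 = 99.5% fall within a 4-week titration.

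**Step 3: year-only rule.** First dose on day y of the year (2 to 365) leaves min(112, 366 − y) affected days.

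- Days 1–112: 253 × 112 + (111 + 110 + … + 1) = 28,336 + 6,216 = 34,552; 34,552 / 40,880 = 84.5%.
- Days 1–126: 239 × 126 + (125 + … + 1) = 30,114 + 7,875 = 37,989; 37,989 / 45,990 = 82.6%.
- Share of the 112-day total falling in days 1–28: 337 × 28 + (27 + … + 1) = 9,436 + 378 = 9,814; 9,814 / 34,552 = 28.4%. An even spread would give 28 / 112 = 25%, so this rule is not concentrated in titration.

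**Step 4: with a first-dose floor.** If the known part of the date matches first dose and the first-dose date is imputed, the on-treatment onset days made pre-treatment fall to 0 in all four scenarios (day missing or year only; 112 or 126 days).

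**Step 5: leverage of one patient.** Fewer than 30 patients in three arms is taken as at most about 10 per arm. One reclassified patient moves an arm's incidence by about 1/10 = 10 percentage points, and the pooled pridopidine column by about 1/20 = 5 points, if that was the patient's only event in the row.

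**The case against.** The strongest reply is that the set of affected events may be empty. The percentages above are shares of possible onset days for events with partial dates, not shares of all AEs, and neither document says how many partial dates there are. Study conduct works against them: time of onset is a required AE item (Protocol 6.5.1.4), AEs are elicited at every visit (6.5.1.3), patients are telephoned during titration and asked about AEs (3.1.2), and data cleaning is planned (8.1). A year-only onset, for events collected only from consent in a study of 21 to 27 weeks, is hard to imagine. This stands, and it limits how much weight the point can bear. It does not defend the rule, which exists only for partial dates and mishandles those that matter.

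Three further limits also stand. An event whose severity increases after first dose remains a TEAE. The overview row for SAEs other than deaths is not worded as treatment-emergent, and all data are listed (SAP section 9), so events leave the summaries but not the report. Some partial-date events in the first-dose month or year truly began before dosing, and the current rule classifies those correctly.

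A reader might go further and infer that TEAEs are in fact under-counted, that every AE table is affected, or that the loss falls mainly on titration under both rules. The documents do not support these readings: the number of partial dates is unknown, one overview row is not restricted to TEAEs, and only about 28% of the year-only rule's affected days over 112 days lie in a 4-week titration.

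**Conclusion.** The point holds as a flaw in the written rule. Followed literally, SAP 15.3 classes as pre-treatment any partial-date event that starts on treatment in the first-dose month (or, if only the year is known, in the first-dose year). The exceptions are a first dose on the 1st (or 1 January) and a later increase in severity. For events that truly began on treatment, the error can only lower TEAE counts.

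TEAEs may therefore be under-counted, by an amount that cannot be computed from the documents and is zero if no start date is partial. The exposure of about 52% of days 1–28 and 13% of days 1–112 (day missing), and about 85% of days 1–112 (year only), rests on evenly spread first doses and onsets. The shifts of about 10 and 5 points per patient rest on an assumed 10 patients per arm, which is an inference from fewer than 30 enrolled, and on the event being the patient's only one in that row. The date logic itself needs none of these assumptions.

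**What to change.** In SAP 15.3, replace the two partial-date rules with one: if the known month and year (or the year, when only that is known) match those of first dose, impute the first-dose date, unless the stop date shows that the event ended before first dose. Otherwise keep the first of the month, or 1 January.

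The cost is one sentence and a small programming change. SAP section 2 says the plan is being finalized before database lock and unblinding, so the change can be made without any appearance of being driven by results.

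The downside should be stated alongside it: truly pre-dose events with a matching partial date and no earlier stop date will be counted as TEAEs. That is the conservative direction for safety, and the one the SAP already accepts for wholly missing dates. Reporting how many AE start dates were imputed, and how many of those decided TEAE status, would show whether either error matters.

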## Statistical Analysis Plan

In the AE summaries, data will be presented in four columns (pridopidine 150 mg BID, pridopidine 100 mg BID, pridopidine total, placebo) using the Safety Population.

The following summaries will be provided. If not stated otherwise, the tables will be sorted in alphabetic order by SOC, and within each SOC, in descending order according to the % of subjects reporting each PT in the pridopidine total group.

- An overall summary of the number and percentage of subjects reporting TEAEs and the number of TEAE events, treatment-related TEAEs, severe TEAEs, TEAEs leading to death (if there are any subjects who died), SAEs other than death, TEAEs leading to study drug discontinuation and TEAEs leading to temporary withdrawal
- The incidence (number and % of subjects) and frequency (event count) of TEAEs broken down by System Organ Class (SOC) and PT.

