The primary endpoint is the mean change from Baseline (Visit 2) to Visit 7/ET in the UDysRS sum score of Parts 1, 3, and 4, in the "ON" state, will be analyzed using a Mixed Model for Repeated Measures (MMRM) with no imputation using the mITT population. The Baseline (Visit 2) score will be included as a covariate and the treatment group (pridopidine 100 mg BID, pridopidine 150 mg BID or placebo), visit (Visit 4, Visit 5, Visit 6, or Visit 7/ET) and the interaction between treatment group and visit as fixed factors in the MMRM. The difference between each dosage of pridopidine vs placebo at Visit 7/ET will be estimated from the MMRM.

Secondary Analysis

The continuous secondary endpoints (sum scores derived from UDysRS, UPDRS, and endpoints based on the “ON/OFF” home diaries) will be analyzed with MMRM models similar to those used for analysis of the primary endpoint. The mITT population will be used for these analyses.

The categorical secondary endpoints (proportion of responders and proportion of patients improving based on PGI-C or CGI-C) will be analyzed in the mITT population using a generalized linear mixed model (using the GLIMMIX procedure from SAS for binomial data with logit link).

PK Analysis

The PK analysis will be conducted on the PK set. Plasma concentrations of pridopidine and its metabolite TV-45065 will be listed and summarized by visit and time point. Descriptive statistics will include the mean, coefficient of variation, geometric mean, minimum, median, and maximum. Relationships between plasma concentrations of pridopidine and TV-45065 at Visit 4, Visit 6, and Visit 7/ET vs key safety and efficacy measures will be explored graphically.

Safety Analysis

The safety analysis will be conducted on the safety set. The treatment-emergent AEs will be coded according to the Medical Dictionary for Regulatory Activities and summarized by treatment group, organ class and preferred term. Further summaries will be done -by seriousness, severity, relationship to study treatment and dose at the time of onset. Other safety endpoints will be summarized with descriptive statistics.

Version and Date of Protocol: 2.0 (Protocol Amendment 1); 19 Nov 2019

S-Figure 1

Study Design

Study week	3-9 weeks				Maintenance														Down titration					
	Up titration				Maintenance																			
Visit (V) #	Screening				Wk 1	Wk 2	Wk 3	Wk 4	Wk 5	Wk 6	Wk 7	Wk 8	Wk 9	Wk 10	Wk 11	Wk 12	Wk 13	Wk 14	Wk 15	Wk 16	Wk 17	Wk 18		

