7.9.4 Safety Analyses

The safety analysis will be conducted on the safety set. The AEs will be coded according to the MedDRA and treatment-emergent adverse events (TEAEs) summarized by treatment group, system organ class and preferred term. Further summaries will be done by seriousness, severity, relationship to study treatment and actual dose at the time of onset.

Vital signs, ECG data and laboratory tests at baseline (last non-missing results prior to the first dose of study drug, each postbaseline visit, and changes from baseline to each of the postbaseline visits will be summarized with descriptive statistics. Shift tables for the laboratory tests based on a classification of values as low, normal, or high with respect to the reference range will be summarized.

For vital signs, orthostatic hypotension is defined as a reduction of 20 mmHg or more in systolic blood pressure, or a reduction of 10 mmHg or more in diastolic blood pressure, for the standing measurement compared to the supine measurement. The proportion of patients with orthostatic hypotension will be summarized with shift tables.

Prilenia Therapeutics

Protocol: PL101-LID201 Protocol Amendment 1/v2.0

Pridopidine

19 Nov 2019

For ECG data, absolute QTcF of >450 msec, >480 msec, and >500 msec, changes from baseline in QTcF>30 msec and <60 msec, and changes in QTcF>60 msec throughout the study will be summarized.

All other safety data will be summarized with descriptive methods.

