### 5.2 Safety Population

The Safety Population will include all subjects receiving at least one dose of study treatment. The subjects will be grouped according to the highest treatment regimen actually reached.. Anyone with mean total daily dose  $> 0$  and  $\leq 100$  mg BID will be included in the 100 mg BID group, anyone with mean total daily dose  $> 100$  mg BID will be included in the 150 mg BID group. The Safety Population will be used for the safety analyses.

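### SAP 15.3 omits the protocol's TEAE summary by actual dose at onset, and SAP 5.2 puts all of a subject's events in one dose column

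*SAP*

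**What the plan says.** **Protocol.** After the SOC and preferred-term tables, section 7.9.4 adds: "Further summaries will be done by seriousness, severity, relationship to study treatment and actual dose at the time of onset". The synopsis makes the same commitment under safety analysis ("relationship to study treatment and dose at the time of onset"). Section 6.5.1.4 puts both dose and time of onset on the AE page of the eCRF.

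**SAP tables.** For AE summaries, SAP 15.3 states that "data will be presented in four columns (pridopidine 150 mg BID, pridopidine 100 mg BID, pridopidine total, placebo) using the Safety Population". It names two outputs: an overall table of counts, and "The incidence (number and % of subjects) and frequency (event count) of TEAEs broken down by System Organ Class (SOC) and PT". The overall table keeps counts of treatment-related, severe and serious events, so three of the protocol's four further classifications survive in some form. Dose at onset does not appear.

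**SAP grouping.** SAP 5.2 first says "The subjects will be grouped according to the highest treatment regimen actually reached". It then gives a cut based on mean total daily dose: anything above zero up to 100 mg BID goes to the 100 mg BID group, anything higher to the 150 mg BID group.

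**Related text.** SAP 4 records that the titration was changed "via Safety Urgent Measures letter to increase the titration period from 2 to 4 weeks". SAP 15.1 breaks exposure down "in titration period (all subjects, subjects with 2 weeks titration, subjects with 4 weeks titration", and likewise for maintenance. SAP 2 and SAP 17 say that the SAP overrides the protocol. SAP 17 does this in one general sentence and does not itemise what was removed.

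**The concern.** Both active arms go through the same 75 mg steps and then a week at 100 mg BID before they diverge. The safety objective is to evaluate 100 mg BID and 150 mg BID against placebo. A column that carries a maintenance-dose label but holds every event a subject had, at whatever dose, mixes start-up intolerance common to both arms with events at the maintenance dose. The dose-at-onset summary was the one planned output that would separate them.

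The SAP 5.2 rules add to this. They have no category below 100 mg BID, so a subject who stops on a 75 mg step is counted at a dose never taken. The two rules can also place the same subject in different columns.

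**Working it through.** There is no planned figure to reproduce. The check has two parts: a comparison of text, and dose-day arithmetic to size the effect.

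**Text.** Dose at onset is planned in protocol 7.9.4 and in the synopsis, and collected under 6.5.1.4. It is absent from the outputs listed in SAP 15.3 and is not mentioned in SAP 17.

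**Inputs (SAP 4.1 and 4.2).**
- Version 1.1 titration: 3 days at 75 mg QD, 4 at 75 mg BID, 7 at 100 mg BID, in total 14 days.
- Version 2.0 titration: 7 days each at 75 mg Q48h, 75 mg QD, 75 mg BID and 100 mg BID, in total 28 days.
- Maintenance: 84 days in both, so the active period is 98 or 112 days. Visit 5 is Day 56 or Day 70.
- Assumption: full adherence.

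**Shares of time.**

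| | Version 1.1 | Version 2.0 |
|---|---|---|
| Days on 75 mg steps, completer | 7/98 = 7.1% | 21/112 = 18.8% |
| Days on 75 mg steps, to Visit 5 | 7/56 = 12.5% | 21/70 = 30% |
| Days before the 150 mg step (150 mg arm), completer | 14/98 = 14.3% | 28/112 = 25% |
| Days before the 150 mg step (150 mg arm), to Visit 5 | 14/56 = 25% | 28/70 = 40% |

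The last two rows include the titration week at 100 mg BID; the first two do not.

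**Where the two SAP 5.2 rules disagree.** Read 100 mg BID as 200 mg/day, and let d be the number of maintenance days taken at 300 mg/day.
- Version 1.1: titration total = 3×75 + 4×150 + 7×200 = 2225 mg. The mean exceeds 200 when (2225 + 300d)/(14 + d) > 200, that is d > 5.75, so from maintenance day 6.
- Version 2.0 with 4 doses in the Q48h week: 4×75 + 7×75 + 7×150 + 7×200 = 3275 mg. (3275 + 300d)/(28 + d) > 200 gives d > 23.25, so from day 24.
- Version 2.0 with 3 doses in that week: total 3200 mg, giving d > 24, so from day 25.

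Example: a version 2.0 subject who stops after 10 days at 150 mg BID has a mean of (3275 + 3000)/38 = 165 mg/day. The highest-regimen rule gives the 150 mg column; the mean-dose rule gives the 100 mg column, together with any event that occurred at 150 mg BID. The SAP does not say whether down-titration days count. They are at 150 mg/day or less, so including them would move the crossing later.

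**The case against.** **Reduced scope.** The trial stopped before 30 subjects were enrolled (SAP 9.3) and is now a proof-of-concept study. Safety output is cut throughout: laboratory summaries to two creatinine parameters, and C-SSRS, QUIP-RS and physical examination to listings. Leaving out one AE table fits that policy. This stands as an explanation, but the SAP does not give it for this table.

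**The data remain.** Dose and onset time are AE form fields, and SAP 9 lists all data. In a trial this small a reader could work through the listing. This stands: what is missing is a summary. The pooled pridopidine column also sets start-up effects against placebo, although mixed with maintenance.

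**The table would be thin.** Fewer than 30 subjects over three arms is about 10 or fewer per arm, and dose at onset is confounded with time on study and with having tolerated earlier steps. This stands too, and limits the table to description.

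**Absence is not fully shown.** The list of tables in SAP 21.1 is not in the text available for review, so a dose-at-onset table there cannot be excluded. SAP 15.3, the section that specifies AE summaries, names none.

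**Stronger readings that the documents do not support.**
- A reader might infer that every titration event in a subject randomised to 150 mg BID lands in the 150 mg column. Under SAP 5.2 a subject who stops during titration goes to the 100 mg column, and the mean-dose rule keeps some early maintenance stoppers there as well.
- A reader might take the 14% to 40% range as the share of time at 75 mg. It includes a week at 100 mg BID; the 75 mg shares are 7% to 30%.
- A reader might infer that a planned AE comparison of the 2-week and 4-week titrations was dropped. Protocol version 2.0 never planned one. The SAP makes that split for exposure only.

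**Conclusion.** The point holds as an unannounced omission that weakens the labelling of the AE columns. Misattribution can go three ways: 75 mg events counted under 100 or 150 mg BID, 100 mg BID titration events counted under 150 mg BID, and, under the mean-dose rule, early 150 mg BID events counted under 100 mg BID.

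The scale is 7% to 19% of a completer's time on 75 mg steps, and 12.5% to 30% of the time to Visit 5. For the 150 mg arm, time before the 150 mg step is 14% to 25% and 25% to 40% respectively. These rest on full adherence and nominal visit days, and say nothing about how many events fall in those days. Early termination makes shorter follow-up plausible, but the documents give no stopping times, so they do not show where in these ranges subjects lie.

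The change is worth making before database lock and unblinding, when the SAP is due to be finalised. It affects how the safety tables can be read, not whether the data exist.

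**What to change.** 1. In SAP 15.3, restore one descriptive TEAE table by actual dose at onset: below 100 mg BID; 100 mg BID; 150 mg BID; down-titration or after last dose. Use subjects and days exposed at each dose as denominators, and show placebo for the matching titration and maintenance periods so that active and placebo are compared over the same stretch of follow-up.
2. In SAP 5.2, reconcile the highest-regimen and mean-dose rules into one. State the unit of the cut in mg/day, whether down-titration days count, and how a subject who never reached 100 mg BID is labelled.
3. If the sponsor prefers not to produce the table, name the omission and its reason in SAP 17.

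Optional: a titration-period AE table by 2-week versus 4-week scheme, using the groups already in SAP 15.1. It would be a new, non-randomised, descriptive output and should be labelled so.

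Cost: SAP wording and one extra table from data already collected. The cells will be small, and dose will be confounded with time on study, so the table should carry no tests.
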